6.3 Treatments

Per protocol, an IV solution of 20mg NA-1/ml will be given to subjects with a body weight < 105 kg to achieve a final target dose of 2.6 mg NA-1/kg. Subjects weighing 105-120 kg will each receive a total dose of 270 mg of study drug (i.e., the entire 13.5 ml contained in the study drug vial). However, per-protocol, at the time of dosing, the total dose is based on the subject's estimated weight if an exact weight is not available. A second weight, using an in-hospital scales, will be obtained by day 5 or discharge (± 1 d). Discrepancies between the weight estimate and actual weight obtained using in-hospital scales may result in some subjects weighing >105 Kg receiving less than 270 mg, and some subjects weighing < 105 Kg receiving the full 270 mg dose. Study drug monitors at each site will record the total volume of NA-1 solution received by each subject and their estimate of body mass at the time of treatment. Two measures of subjects' NA-1 exposure and 4 additional subject-level measures of the timeliness of the interventions will be computed as follows.

1. Number subjects who received any NA-1
2. Descriptive statistics for:
 - a. Time from randomization to start of NA-1 infusion
 - b. Time from NCCT to start of NA-1 infusion
 - c. Subject's Actual exposure (mg NA-1/kg body wt) =
[(20mg NA-1/ml of IV solution)*ml dose received]/kg body wt, where "kg body weight" was obtained using an in-hospital scale.
 - d. Subject's Relative exposure (%) =
(Actual exposure*2.6 mg NA-1/kg body wt) *100. where "kg body weight" was obtained using an in-hospital scale.
 - e. Time from NCCT to 1st recanalization
 - f. Time from NCCT to arterial access puncture

An additional 7 measures of overall dosing compliance and timeliness of intervention, at the treatment group level, will be computed from the subject-level measures and reported as percentages of the number of subjects in each treatment arm who received NA-1 therapy or placebo.

3. Overall relative NA-1 dosing compliance (%)= $100*[A+B]/C$ where A = number of subjects who received 2.6 mg NA-1/kg body wt; B = number of subjects who received 270mg total dose; C = number of subjects who received any amount of NA-1. As dosing compliance (per protocol) is the subject of this calculation, "kg

- body wt” in this instance will be the weight (actual or estimated) obtained at the time of dosing.
4. Speed of intervention metrics measured on NA-1 and placebo treated subjects (% of each treatment group):
 - a. % of subjects with time from randomization to NA-1 or placebo infusion < 30 minutes
 - b. % of subjects with time from NCCT to infusion with NA-1 or placebo infusion < 60 minutes
 - c. % of NA-1 and placebo subjects with time from NCCT to recanalization < 75 minutes
 - d. % of NA-1 and placebo subjects with time from NCCT to recanalization < 90 minutes
 - e. % of NA-1 and placebo subjects with time from NCCT to arterial access puncture <45 minutes
 - f. % NA-1 and placebo subjects with time from NCCT to arterial access puncture <60 minutes

All measures will be summarized separately for the ITT, PP, and safety populations; individual exposures and speed of intervention times will be listed by treatment arm and subject.

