7.3 Exclusion Criteria

- 1) Evidence of a large core of established infarction defined as ASPECTS 0-4.
- 2) Evidence of absence of collateral circulation on CTA (Collateral score of 0 or 1).
- 3) Intent to use any endovascular device other than a stent retriever or clot aspiration device or intra-arterial medications as the initial thrombectomy approach.
- 4) Intent to use any intravenous thrombolytic other than alteplase if intravenous thrombolysis is planned.
- 5) No femoral pulses, very difficult endovascular access or extreme tortuosity of the great vessels that is predicted to result in an inability to timely deliver endovascular therapy. Direct common carotid or radial/brachial/axillary access is permissible.
- 6) Estimated or known weight > 120 kg or < 45 kg.
- 7) Pregnancy; if a woman is of childbearing potential a urine or serum β -hCG test is positive, or breastfeeding.
- 8) Severe contrast allergy or absolute contraindication to iodinated contrast preventing endovascular intervention including any contraindications listed in the prescribing information approved by local authorities (e.g., patients with decompensated heart failure as a contraindication for the use of VISIPAQUE™ 270 in Germany).
- 9) Clinical history, past imaging or clinical judgment suggests that the intracranial occlusion is chronic or there is suspected intracranial dissection such that there is a predicted lack of success with endovascular intervention.

- 10) Prior enrolment in the ESCAPE-NA1 trial or prior receipt of NA-1 for any reason.
- 11) Severe known renal impairment defined as requiring dialysis (hemo- or peritoneal) or if known creatinine clearance < 29 mL/min.
- 12) Patient has a severe or fatal comorbid illness that will prevent improvement or follow-up.
- 13) Patient cannot complete follow-up treatment due to co-morbid non-fatal illness or they are a visitor to the city or any other known reason that follow-up would be impossible (e.g. incarcerated in a federal prison).
- 14) Participation in another clinical trial investigating a drug, medical device, or a medical procedure in the 30 days preceding study inclusion.

This population is expected to consist of subject very similar to those treated in the ESCAPE trial.³

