8.1.1.2 Dose Administration

Dosing will be carried out by, or under the supervision of, the trial physician who is supervising the care of the subject for the planned or ongoing endovascular reperfusion procedure.

A syringe for each individual subject dosing will be prepared by calculating the volume to draw from the vial as follows: for subjects weighing less than 105 kg: $(2.6 \text{ mg/kg} \times \text{subject weight in kg}) / (20 \text{ mg/ml})$. This will determine the number of mL to pull up into the syringe. For subject weighing 105-120 kg the full volume of one vial (13.5mL, equivalent to 270 mg of NA-1) will be used.

The syringe containing study drug will be injected into the intravenous port of a 50 or 100 mL drip bag of 0.9% normal saline that has been labeled with the randomization number and subject's age. The bag will be mixed by squeezing and inverting the bag several times. After dilution into the drip bag, the drug is stable for up to 5 hours, however it should be infused into the subject as soon as practical with a target randomization to treatment time of 30 minutes or less.

An appropriate sized syringe must be used, such that this volume is between 20% and 100% of the delineated markers on the syringe. Once a volume of drug has been drawn into the syringe, the vial will be marked as "used" and placed into a separate vial storage area.

Dosing will be performed by administering the contents of the bag of study drug to the subject through an intravenous catheter inserted into a vein in the upper or lower extremity and using a standard infusion pump. Dosing will be carried out evenly over the course of 10 ± 1 minutes while the intravenous bag contents are administered to the subject. The entire volume (treatment dose) of the intravenous mini-bag must be administered.

After the dose administration, a minimum of 10 mL of saline will be administered using the infusion pump, to flush any remaining medication left within the intravenous tubing. This method of dose administration is identical to that previously conducted in the Phase 2 ENACT trial¹¹. In the event that a subject is concomitantly receiving alteplase therapy, dose administration of NA-1 will be conducted through a separate intravenous catheter inserted into an extremity not containing the alteplase line. If alteplase therapy has been completed, the same intravenous catheter may be used after it has been flushed with saline.

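### SAP 6.3 item 2d multiplies actual exposure by the 2.6 mg/kg target instead of dividing by it, so a subject dosed exactly at target is reported at 676%

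*SAP*

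**What the plan says.** SAP section 6.3 (Treatments) sets out how exposure to NA-1 will be described. For subjects under 105 kg the solution is given "to achieve a final target dose of 2.6 mg NA-1/kg". For heavier subjects the dose is fixed: "Subjects weighing 105-120 kg will each receive a total dose of 270 mg of study drug". The section explains that dosing may rest on an estimated weight and that a later in-hospital weight may differ from it.

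Two subject-level exposure measures follow, both using the in-hospital weight:

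- Item 2c, "Subject's Actual exposure (mg NA-1/kg body wt"), is the concentration times the volume received, divided by weight: [("20mg NA-1/ml of IV solution)*ml dose received]/kg body wt".
- Item 2d, "Subject's Relative exposure" (%), is ("Actual exposure*2.6 mg NA-1/kg body wt) *100".

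The section closes by requiring all its measures to be summarized separately for the ITT, PP and safety populations, with individual exposures listed by treatment arm and subject.

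**The concern.** Item 2c already delivers a dose per kilogram. Expressing it relative to target means dividing by the target in the same units, so that the units cancel and a subject on target scores 100. Item 2d multiplies two mg/kg quantities. The result is not a percentage, and 100 no longer marks the target.

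This measure is meant to show how far the dose received departed from target once the true weight is known. It is the only listed measure that expresses the departure as a percentage of target on the in-hospital weight. The group-level compliance figure in item 3 deliberately uses the weight available at dosing, so it cannot show error from estimated weights. If item 2d is programmed as written, the relative-exposure summaries are wrong in all three populations, and so are any listings that carry the measure. A programmer who notices the slip has to depart from the SAP without written authority.

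**Working it through.** **Inputs**

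- Target dose: 2.6 mg/kg (SAP 6.3).
- Concentration: 20 mg/mL (SAP 6.3, item 2c; Protocol 8.1.1.2).
- Volume rule, "for subjects weighing less than 105 kg": 2.6 × weight / 20 mL (Protocol 8.1.1.2).
- Maximum dose: 270 mg, one full 13.5 mL vial, at 105–120 kg (SAP 6.3; Protocol 8.1.1.2).
- Weight limits, as an exclusion: "Estimated or known weight > 120 kg or < 45 kg" (Protocol 7.3).

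The SAP gives no numerical value for relative exposure, so there is no figure of its own to reproduce. The dose inputs agree with each other: 13.5 mL × 20 mg/mL = 270 mg.

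**Formulas**

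- Actual exposure: A = 20 × mL / kg, in mg/kg.
- As written: A × 2.6 × 100, in (mg/kg)².
- By division: (A / 2.6) × 100, a pure percentage.

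**Subject dosed at target.** At 80 kg the volume is 2.6 × 80 / 20 = 10.4 mL, so A = 20 × 10.4 / 80 = 2.6 mg/kg. As written: 2.6 × 2.6 × 100 = 676. By division: 2.6 / 2.6 × 100 = 100. The result is the same at 45, 70 and 100 kg, because weight cancels.

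**Size of the error for any subject.** (A × 2.6 × 100) / (A / 2.6 × 100) = 2.6² = 6.76, whatever A is.

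**What a printed 100 would mean.** A × 2.6 × 100 = 100 requires A = 1 / 2.6 = 0.385 mg/kg, which is 0.385 / 2.6 = 14.8% of target.

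**Examples.** A dose drawn up for an estimated 80 kg is 10.4 mL × 20 = 208 mg. The last three rows are subjects who correctly received 270 mg.

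| Subject | A (mg/kg) | As written | By division |
|---|---|---|---|
| At target | 2.6 | 676 | 100% |
| Half dose | 1.3 | 338 | 50% |
| Estimated 80 kg, true 70 kg | 208/70 = 2.971 | 772.6 | 114.3% |
| Estimated 80 kg, true 90 kg | 208/90 = 2.311 | 600.9 | 88.9% |
| 105 kg, 270 mg | 270/105 = 2.571 | 668.6 | 98.9% |
| 110 kg, 270 mg | 270/110 = 2.455 | 638.2 | 94.4% |
| 120 kg, 270 mg | 270/120 = 2.25 | 585.0 | 86.5% |

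**Could the operator be a text-extraction fault?** This cannot be excluded outright, but it is unlikely. The same section prints the slash for division in items 2c and 3 and uses the asterisk for multiplication throughout. No other part of either document gives a different formula.

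**The case against.** The strongest reply is that the slip is harmless. The label says percent, the line above is in mg/kg, and the target is stated in the same section, so the intended ratio is obvious. A listing full of values near 676 would be caught in any output check. The measure is descriptive: it appears neither in the table of inferential efficacy analyses nor in the safety analyses, and the compliance figure in item 3 does not use it. The dose-related examples of major protocol deviations in SAP 6.2 are a missing or incomplete dose, a wrong vial, or an infusion of 15 minutes or more, none of which depends on item 2d. Item 2c is correct, and item 2d only rescales it by a constant, so no information is lost.

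All of that stands, and it limits the weight of the point. It does not make the written definition right: following the SAP exactly still produces wrong tables.

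Two further observations also stand. The 676 figure belongs to subjects at 2.6 mg/kg. Those correctly given 270 mg at 105–120 kg would show about 669 down to 585, although the factor 6.76 applies to them too. Division alone would then show these subjects at 98.9% down to 86.5% although dosed as specified, mixing the effect of the maximum dose with error from estimated weights.

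**Conclusion.** The formula is wrong as written. It inflates every relative exposure by a factor of 6.76, and a subject at exactly 2.6 mg/kg is reported at 676% instead of 100%. The conclusion rests only on the units given in items 2c and 2d and on 2.6 mg/kg being the reference, which the section itself states. The consequence is confined to descriptive exposure output. No hypothesis test, population definition or decision rule is affected. It should be corrected before the exposure tables and listings are programmed.

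**What to change.** Rewrite item 2d as: Relative exposure (%) = (Actual exposure / 2.6 mg NA-1 per kg body weight) × 100, keeping the in-hospital weight as the denominator of actual exposure. This changes one operator and needs no new data.

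As an optional addition, one sentence could say whether relative exposure for subjects in the 270 mg group is reported against 2.6 mg/kg or against the 270 mg maximum. If it is reported against 2.6 mg/kg, a footnote should say that values below 100% are expected in that group. This concerns how exposure is reported and does not bear on the dose. Any table or listing programs already written should be checked against the corrected text.

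### The SAP's dosing-compliance percentage counts any 270 mg dose as compliant whatever the dosing weight, and its 2.6 mg/kg term has no tolerance, so the figure is not well defined

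*SAP*

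**What the plan says.** SAP 6.3 (Treatments) restates the dosing rule. Lighter subjects are dosed at 2.6 mg/kg from a 20 mg/mL solution. For the heavier band it says: "Subjects weighing 105-120 kg will each receive a total dose of 270 mg of study drug". Protocol 8.1.1.2 makes the same split. It gives the weight formula "for subjects weighing less than 105 kg" and a whole vial ("13.5mL, equivalent to 270 mg of NA-1") from 105 to 120 kg.

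Item 3 of SAP 6.3 then defines overall dosing compliance as 100 × (A + B) / C:

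- The first term counts those given the weight-based dose: "A = number of subjects who received 2.6 mg NA-1/kg body wt".
- The second term counts those given the full vial: "B = number of subjects who received 270mg total dose".
- The denominator, C, is everyone in whom NA-1 was given at all, whatever the quantity.

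The item closes by saying that body weight "in this instance will be the weight (actual or estimated) obtained at the time of dosing". Body weight appears in A only, so that sentence does not restrict B. Neither document gives a tolerance or a volume-rounding rule for A.

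**The concern.** The percentage is meant to show how far dosing followed the protocol. The protocol ties 270 mg to a weight band, but B credits 270 mg at any weight. Each subject is assigned one vial (Protocol 8.1.1.1), so the excess that B scores as compliant is the largest that vial can deliver.

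A has a different problem. Its result depends on how literally 2.6 is taken, and the SAP does not say. Two programmers could follow the text faithfully and report very different compliance figures.

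What is at stake is the credibility of one descriptive number on exposure. It is worth getting right because Protocol 4.4.1 reports that the highest Phase 1 dose was 3.75 mg/kg and that the two highest dose groups had more adverse events than the lower ones. A full vial exceeds 3.75 mg/kg at any weight below 270 / 3.75 = 72 kg.

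**Working it through.** **Inputs.** Target 2.6 mg/kg, solution 20 mg/mL, vial 13.5 mL, cut-off 105 kg (Protocol 8.1.1.2, SAP 6.3). Eligible weight is 45 to 120 kg (Protocol 7.3). The syringe step is not given, so it is an assumption shown as a range.

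**The plan's own figure.** 13.5 mL × 20 mg/mL = 270 mg. It reproduces exactly. The weight formula is 2.6 / 20 = 0.13 mL per kg.

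**Term B.** A full vial at dosing weight w gives 270 / w mg/kg:

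| Dosing weight | mg/kg | % of 2.6 | Counted in B |
|---|---|---|---|
| 45 kg | 6.00 | 231 | yes |
| 60 kg | 4.50 | 173 | yes |
| 80 kg | 3.38 | 130 | yes |
| 100 kg | 2.70 | 104 | yes |

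By contrast, 250 mg at 60 kg is 250 / 60 = 4.17 mg/kg. It meets neither A nor B and is non-compliant. B therefore masks full-vial errors only, and the larger error passes while the smaller one fails.

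**Term A read as exactly 2.6.** At 71 kg the formula gives 71 × 0.13 = 9.23 mL. Drawing 9.2 mL gives 9.2 × 20 / 71 = 2.592 mg/kg, which fails. Over the 59 whole-kg weights from 45 to 103 kg, with 0.13 × weight rounded to the syringe step, the numbers passing are:

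| Assumed step | Exactly 2.6 | 2.55 to under 2.65 |
|---|---|---|
| 0.01 mL | 59 | 59 |
| 0.1 mL | 6 | 59 |
| 0.2 mL | 3 | 59 |
| 0.5 mL | 2 | 43 |
| 1.0 mL | 1 | 22 |

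**Term A read to one decimal.** A 270 mg dose lies between 2.55 and 2.65 mg/kg when the weight is between 270 / 2.65 = 101.9 kg and 270 / 2.55 = 105.9 kg. Such a subject meets both A and B. At 105 kg the full vial that the protocol specifies gives 270 / 105 = 2.57 mg/kg, so that subject adds two to the numerator and one to C. With high compliance elsewhere, A + B can exceed C.

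**Illustration, all inputs assumed.** Take 560 subjects given NA-1: 28 correctly on the full vial, 10 full-vial errors at low weight, and 522 correctly dosed with 0.1 mL rounding and whole-kg weights spread evenly over 45 to 103 kg.

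- A exact: (28 + 10 + 522 × 6/59) / 560 = 16.3%.
- A to one decimal, ignoring any double count: (28 + 10 + 522) / 560 = 100%.
- One classification per subject against the protocol volume: (28 + 522) / 560 = 98.2%.

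**The band just below 105 kg.** 270 / 2.6 = 103.85 kg. Between that weight and 105 kg the weight formula asks for more than the vial holds and more than the 270 mg maximum. At 104 kg it gives 104 × 0.13 = 13.52 mL, against 13.5 mL.

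**The case against.** **Context supplies the missing condition.** SAP 6.3 opens with the two dosing bands, and item 3 says it concerns compliance with the protocol, so A and B plainly stand for those bands. That is probably the intent. It does not settle the matter, because the definition that will be programmed has no such condition and the weight sentence does not reach B.

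**Excess doses are visible elsewhere.** This stands. Item 2c reports actual mg/kg on in-hospital weight, the default summaries in SAP 6.0 include the maximum, and SAP 6.3 lists individual exposures by arm and subject. A reader might infer that the plan hides overdoses from the trial's reporting; the documents do not support that. Two other safeguards are weaker. Item 2d is written as a multiplication by 2.6, which gives 2.6 × 2.6 × 100 = 676% for an on-target subject. The deviation examples in SAP 6.2 name a missing or incomplete dose but not an excess, although that list is open-ended.

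**The two faults in A need different readings.** This also stands. On the exact reading, overlap with B requires a weight of exactly 270 / 2.6 kg, so practically nobody is counted twice. On the one-decimal reading the 71 kg failure disappears. A reader might infer that the formula is certain to fail correctly dosed subjects. That holds only on the exact reading and with a coarse enough syringe step. What can be said is that neither reading gives a sound measure.

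**The SAP already expects some light subjects to get a full vial.** It foresees "some subjects weighing < 105 Kg receiving the full 270 mg dose". A reader might take this as evidence that dosing errors are scored as compliant. It is not. That sentence concerns error in the estimated weight, and item 3 deliberately judges compliance on the dosing weight, so those subjects are compliant by design.

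**Conclusion.** The point holds as a defect in one descriptive percentage. That B lacks a weight condition follows from the text and needs no assumption. Its effect is to score a full vial as compliant at any dosing weight, up to 6.0 mg/kg at 45 kg; excesses short of a full vial are not masked. The fault in A is a missing tolerance. How much that matters depends on the unstated reading and on the syringe step: with 0.1 mL steps, 53 of 59 whole-kg weights fail on the exact reading and none on the one-decimal reading, which instead double counts 270 mg recipients between about 101.9 and 105.9 kg.

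Nothing in the documents suggests that full-vial errors are common, and the 16.3%, 100% and 98.2% figures only illustrate the spread. Item 3 does not enter the primary ITT analysis or the alpha allocation, and per-protocol membership is set by a separate blinded review of deviations (SAP 2.3). This is a minor wording repair, not a threat to the trial's conclusions.

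**What to change.** First reconcile three statements that disagree between about 103.85 and 105 kg: the weight formula below 105 kg, the 105 kg cut-off for the whole vial, and the 270 mg maximum (Protocol 8.1.1.2 and SAP 6.3). This review does not say which should govern. Restricting B to 105 kg and above without that step would leave a 104 kg subject given 270 mg outside B, and outside A too if A stays exact.

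Then replace item 3 with a single yes/no for each NA-1 recipient: recorded volume compared with the reconciled protocol volume for the dosing weight, within a tolerance that the sponsor states before unblinding. If A and B are kept as components, make B conditional on dosing weight and the two mutually exclusive. Report doses above the tolerance separately from those below it.

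As a check on feasibility, a 5% tolerance would pass all 59 whole-kg weights at steps up to 0.5 mL, and either 5% or 10% would reject the full vial at 45, 60 and 80 kg.

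The cost is SAP wording and a few lines of programming. Dose volume and subject weight are already recorded (Protocol 6.5, SAP 6.3), so no new data are needed.

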6.4 Demographic and Baseline Characteristics

Subject demographic and baseline characteristics will be summarized with descriptive statistics for each treatment group. Demographic variables include, but are not limited to: age, sex, race-ethnicity, weight at time of dosing (in kg), and weight as determined in hospital (in kg). Baseline characteristics include but are not limited to: prior use of alteplase (tPA), intended first thrombectomy approach (stent retriever or thrombus aspiration device), baseline NIHSS score, baseline ASPECTS score, occlusion location, and site. The summaries will be provided for both the ITT and Per Protocol populations. Inferential statistics (i.e., p-values or CI) will not be provided for these data with the exception of the results of a Fisher’s Exact Test which will be performed for the two stratification variables “alteplase use” (yes/no), and “first declared thrombectomy device” (stent retriever / aspiration device) in order to assess balance across treatment groups.

